8.9 Source Data

Source documents are original documents, data, and records from which participants' CRF data are obtained. These include, but are not limited to, hospital records (from which medical history and previous and concurrent medication may be summarised into the CRF), clinical and office charts, laboratory and pharmacy records, diaries, microfiches, radiographs, computed tomographic or ultrasound scans, and correspondence with primary or secondary care. CRF entries will be considered source data if the CRF is the site of the original recording (e.g., there is no other written or electronic record of data). All documents will be stored safely in confidential conditions. On all study-specific documents, other than the signed consent, the participant will be referred to by the study participant number/code, not by name. All research team members taking part in either the qualitative or quantitative parts of the study will have received Good Clinical Practice (GCP) training; the PI at each site is responsible for delivering the required training and ensuring everyone is up to date with regulatory requirements as per GCP.

CONFIDENTIAL Page 20 of 35 IRAS: 299307

9. TREATMENT OF STUDY PARTICIPANTS

9.1 Description of Study Treatment

Patients will not receive any additional treatment as a result of taking part in this research. All patients taking part in this research will already have been offered treatment with intravascular lithotripsy (Shockwave) as part of their standard NHS care.

9.2 Storage of Study Equipment or Related apparatus

The intravascular lithotripsy (Shockwave) catheters will be stored as per standard NHS principles and guidance at each NHS site.

CONFIDENTIAL Page 21 of 35 SHOCC Study IRAS: 299307

10. SAFETY REPORTING

10.1 Definitions

10.1.1 Adverse Event (AE)

An AE or adverse experience is:

Any untoward medical occurrence in a patient or clinical investigation participants, which does not necessarily have to have a causal relationship with this treatment.

An AE can therefore be any unfavourable and unintended sign (including an abnormal laboratory finding), symptom or disease temporally associated with the study, whether or not considered related to the study.

10.1.2 Adverse Reaction (AR)

All untoward and unintended responses related to the study.

All cases judged by either the reporting medically qualified professional or the sponsor as having a reasonable suspected causal relationship to the study qualify as adverse reactions.

10.1.3 Severe Adverse Events

To ensure no confusion or misunderstanding of the difference between the terms "serious" and "severe", which are not synonymous, the following note of clarification is provided:

The term "severe" is often used to describe the intensity (severity) of a specific event (as in mild, moderate, or severe myocardial infarction); the event itself, however, may be of relatively minor medical significance (such as severe headache). This is not the same as "serious," which is based on patient/event outcome or action criteria usually associated with events that pose a threat to a participant's life or functioning. Seriousness (not severity) serves as a guide for defining regulatory reporting obligations.

10.1.4 Serious Adverse Event or Serious Adverse Reaction

A serious adverse event or reaction is any untoward medical occurrence that at any dose:

- Results in death,
- Is life-threatening,

NOTE: The term "life-threatening" in the definition of "serious" refers to an event in which the participant was at risk of death at the time of the event; it does not refer to an event which hypothetically might have caused death if it were more severe.

- Requires inpatient hospitalisation or prolongation of existing hospitalisation,
- Results in persistent or significant disability/incapacity, or
- Is a congenital anomaly/birth defect.
- Other important medical events*

*Other events that may not result in death, are not life threatening, or do not require hospitalisation, may be considered a serious adverse event when, based upon appropriate medical judgement, the event may jeopardise the patient and may require medical or surgical intervention to prevent one of the outcomes listed above.

10.1.5 Expected Serious Adverse Events/Reactions

This study follow established international guidance (including NHS and NICE guidance) as to what constitutes best medical therapy for PAD, and we therefore do not expect major issues with serious adverse events or reactions. Standard care NHS pathways will be followed. Minor bleeding such as bruising is expected in patients who are on therapy with an antiplatelet agent such as clopidogrel.

CONFIDENTIAL Page 22 of 35 SHOCC Study IRAS: 299307

Further, myalgia might be associated with high-dose statin therapy. These are the two most common adverse reactions which we might expect in this patient group.

10.1.6 Suspected Unexpected Serious Adverse Reactions

A serious adverse reaction, the nature or severity of which is not consistent with the applicable product information.

10.2 Reporting Procedures for All Adverse Events

All AEs occurring during the study observed by the investigator or reported by the participant, whether or not attributed to study, will be recorded on the CRF.

The following information will be recorded: description, date of onset and end date, severity, assessment of relatedness to study, other suspect device and action taken. Follow-up information should be provided as necessary.

AEs considered related to the study as judged by a medically qualified investigator or the sponsor will be followed until resolution or the event is considered stable. All related AEs that result in a participant's withdrawal from the study or are present at the end of the study, should be followed up until a satisfactory resolution occurs.

It will be left to the investigator's clinical judgment whether or not an AE is of sufficient severity to require the participant's removal from treatment (see section 7.7). A participant may also voluntarily withdraw from treatment due to what he or she perceives as an intolerable AE. If either of these occurs, the participant must undergo an end of study assessment and be given appropriate care under medical supervision until symptoms cease or the condition becomes stable.

The severity of events will be assessed on the following scale: 1 = mild, 2 = moderate, 3 = severe. The relationship of AEs to the study will be assessed by a medically qualified investigator.

10.3 Reporting Procedures for Serious Adverse Events (SAEs) and Serious Adverse Reactions (SARs)

SAEs, with the exception of expected SAEs and SARs, must be reported to the Sponsor within one working day of discovery or notification of the event. The Sponsor will perform an initial check of the information and ensure that it is reviewed at the next R&D Management meeting. All SAE information must be recorded on an SAE form and sent to the Sponsor using the appropriate reporting form and the contact details on there. Additional information received for a case (follow-up or corrections to the original case) needs to be detailed on a new SAE form which must be sent to the Sponsor using the appropriate reporting form and the contact details on there.

The Sponsor will report all SUSARs to the Research Ethics Committee concerned. Fatal or life-threatening SUSARs must be reported within 7 days and all other SUSARs within 15 days. The CI will inform all investigators concerned of relevant information about SUSARs that could adversely affect the safety of participants.

In addition to the expedited reporting above, the CI shall submit once a year throughout the study or on request an Annual Report to the Ethics Committee which lists all SAEs / SUSARs that have occurred during the preceding 12 months.

CONFIDENTIAL Page 23 of 35 SHOCC Study IRAS: 299307

11. STATISTICS

11.1 Description of Statistical Methods

This is a non-randomised prospective observational multicentre cohort study.

We will report descriptive statistics for all parameters of interest, including mean and standard deviation with 95% confidence interval (CI) for normally distributed variables and median values with interquartile range(s) for non-normally distributed variable.

Standard tests will be used to assess differences between categorical and non-categorical variables of interest.

The analyses will be overseen by the CI and the Bioinformatics Hubs within the Department of Cardiovascular Sciences, University of Leicester.

Results will be presented in tabular format where possible.

11.2 The Number of Participants

We will record clinical characteristics for 60 patients treated with intravascular lithotripsy in the participating NHS centres over the period of one year. We will follow-up patients for six months. We expect a total of 60 patients to complete follow-up during this period of time, providing full clinical and imaging data, based on our national audits and UK PAD data for 2019-2021 based on the National Vascular Registry and the Vascular and Endovascular Research Network.

For the imaging sub-study (which is only taking part in Leicester i.e. the main study site), we have used a total of 182 patients' data (with femoro-popliteal disease) to estimate the sample size required, based on a study which is ongoing (using this type of plaque analysis for femoro-popliteal plaques). These 182 patients had their plaques analysed using the same technique that we are planning to use in this instance, prior to plain balloon angioplasty. Based on that data, we estimate a mean volume of 1.22mm3 for the calcified part of the femoro-popliteal plaque (based on Hounsfield units) and a standard deviation of 0.4 units; with the assumption we will document a reduction of the calcified component to 0.61 mm3 and to document this within a standard deviation of 0.4 units with a power of 90% and an alpha set at 0.05, we will require 20 patients to take part in this imaging sub-analysis.

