8.3.3 Optional Sub-study

A total of 20 consecutive patients will be invited to take part in sub-group analysis to document the impact of the intravascular lithotripsy on the calcified component of the atherosclerotic plaque. These patients will be recruited from the main site, University Hospitals of Leicester. We will stop recruiting in this sub-analysis once 20 patients have been recruited and have had their second CT scan three days after their intravascular lithotripsy procedure.

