11.3 The Level of Statistical Significance

A p value of <0.05 will be regarded as statistically significant.

11.4 Criteria for the Termination of the Study.

Given that this is an observational study which is recruiting patients who undergo a treatment that is already available in the NHS, we do not have specific stoppage criteria at this point in time. A Data Safety Monitoring Committee (DSMC) will convene at regular intervals, chaired by an independent specialist.

11.5 Procedure for Accounting for Missing, Unused, and Spurious Data.

The PI will be contacted at each site in case of missing or spurious data to ensure that the information collected is precise.

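### The imaging sub-study's 20 patients and 90% power do not follow from a paired before/after calculation; the mismatch is conservative, so the justification needs restating but the number does not

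*Protocol*

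**What the plan says.** Protocol section 11.2 sizes the imaging sub-study from an ongoing study of 182 patients with femoro-popliteal disease. From those data "we estimate a mean volume of 1.22mm3 for the calcified part of the femoro-popliteal plaque", with an SD of 0.4. The target is set "with the assumption we will document a reduction of the calcified component to 0.61 mm3", and the paragraph concludes, with "a standard deviation of 0.4 units with a power of 90% and an alpha set at 0.05, we will require 20 patients". On the source of the inputs it says: "These 182 patients had their plaques analysed using the same technique that we are planning to use in this instance, prior to plain balloon angioplasty". It names no test, number of groups, sidedness, before/after correlation or SD of change. Section 11.3 adds only "A p value of <0.05 will be regarded as statistically significant".

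The design is described elsewhere. Section 8.3.1 provides for plaque analysis of each patient's routine baseline CT. Section 8.3.3 describes a single consecutive series at the main site, with recruitment ending "once 20 patients have been recruited and have had their second CT scan three days after their intravascular lithotripsy procedure". No comparison group appears anywhere in the protocol. Section 14.7 acknowledges that the second scan involves additional radiation.

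**The concern.** Each patient supplies two measurements of the same plaque, so the comparison is paired. Its power is governed by the SD of the change within a patient. The 182 source patients contributed scans taken before angioplasty only, so their SD describes how patients differ from one another. It says nothing direct about how much one patient's value changes.

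This is the protocol's only power statement; the 60 in the main study is an expected recruitment figure. It is also the stated reason why 20 patients should have a non-routine CT. If the calculation does not match the design, an ethics committee or later reader is given the wrong account of what 20 patients can show.

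**Working it through.** **Inputs (section 11.2).** Difference 1.22 − 0.61 = 0.61 mm3, a 50% reduction. SD 0.4, power 90%, alpha 0.05. Two-sided testing is assumed, because sidedness is not stated.

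**Step 1: reproduce the 20.** For two independent groups by the normal formula:

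n per group = 2 × (1.96 + 1.2816)² × 0.4² / 0.61² = 2 × 10.508 × 0.16 / 0.3721 = 9.04

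Rounded up, this is 10 per group, or 20 in total. By noncentral t (18 df, noncentrality 0.61 / (0.4 × √(2/10)) = 3.41), power at 10 + 10 is 89.7%. This reproduces the stated figures to rounding.

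**Step 2: try the paired formula with 0.4 as the SD of change.** With 7 patients the noncentrality is 0.61 / (0.4/√7) = 4.03 on 6 df, and power is 91.6%. With 6 patients it is 84.4%. The answer is therefore 7, not 20.

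**Step 3: paired formula with 0.4 as the SD at each scan.** The SD of change is 0.4 × √(2(1 − r)), where r is the before/after correlation. The protocol gives no r, so a range is shown. The SD is assumed equal at both scans. Power is by noncentral t with n − 1 df.

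| r | SD of change | Pairs for 90% power, fall of 0.61 | Power with 20 pairs, fall of 0.61 | Fall detectable with 20 pairs at 90% power |
|---|---|---|---|---|
| −1 | 0.800 | 21 | 89.9% | 0.61 mm3 (50%) |
| −0.5 | 0.693 | 16 | 96.2% | 0.53 mm3 (43%) |
| 0 | 0.566 | 12 | 99.5% | 0.43 mm3 (35%) |
| 0.3 | 0.473 | 9 | 99.98% | 0.36 mm3 (30%) |
| 0.5 | 0.400 | 7 | >99.99% | 0.31 mm3 (25%) |
| 0.8 | 0.253 | 5 | >99.99% | 0.19 mm3 (16%) |

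Percentages in the last column are of the 1.22 mm3 baseline mean.

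**Step 4: what would make the stated figures right for pairs?** At 90% power, 20 pairs detect 0.764 times the SD of change. Setting this equal to 0.61 gives an SD of change of 0.61 / 0.764 = 0.80, twice the stated SD. With SD 0.4 at both scans this needs r close to −1, which is not credible for one plaque scanned twice within days. If the SDs differ and r = 0, the post-procedure SD would have to reach √(0.80² − 0.4²) = √0.48 ≈ 0.69.

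**Step 5: dropout.** No allowance is stated that could raise a smaller number to 20, and section 8.3.3 recruits until 20 patients have had the second scan.

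**The case against.** The protocol never says that it used a two-group formula. The match at 10 + 10 is also not perfect: exact t gives 89.7%, and 11 + 11 would be needed to pass 90%. A paired calculation with an SD of change near 0.80 also lands at about 20. This stands. The two-group origin is an inference, and the firm statement is only that the stated inputs do not give 20 under a paired calculation.

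A reader might infer from a wrong sample-size formula that the sub-study is underpowered. The figures show the opposite for any correlation of 0 or more, and power is still 96% at −0.5.

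A reader might also infer that the 0.61 mm3 reduction is itself an error. It is a declared assumption, not a claimed smallest detectable effect, and nothing in the protocol shows it to be wrong. What fails is the link between 20 patients, 90% power and that fall.

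Finally, it is tempting to say that an unpaired test is planned and would discard the within-patient information. Section 11.1 promises only standard tests, and the choice of test may properly sit in a statistical analysis plan that is not shown. The protocol specifies no unpaired analysis.

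It is also fair to say that keeping 20 when 5 to 12 pairs would meet the stated target risks fitting a new reason to a fixed number. The restated paragraph should therefore say openly what 20 pairs can detect, so that the number of additional scans can be judged on that basis.

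**Conclusion.** The point holds in a limited form. The claim that 20 patients give 90% power for a fall from 1.22 to 0.61 mm3 does not fit a single-group before/after design, and the SD used is not the SD that such a design needs. A matching calculation asks for 7 patients if 0.4 is the SD of change, or 12, 7 and 5 at correlations of 0, 0.5 and 0.8. With 20 pairs, power for 0.61 is at least 99.5% at any correlation of 0 or more.

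The correlation-based figures rest on two assumptions that the protocol does not supply: the range of correlation, and an SD of 0.4 at both scans. The direction is less sensitive, because power for 0.61 falls to 90% only if the SD of change reaches about 0.80.

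The error is conservative and threatens no conclusion. It concerns an optional, single-site sub-study serving one secondary objective, and leaves the primary outcome and the 60-patient cohort untouched. It should be fixed because it is the only stated power and the stated basis for the number of patients given an extra CT. It is not grounds for holding up the study.

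**What to change.** Keep 20 and rewrite the sub-study paragraph of section 11.2:

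- State that the comparison is within patient, between the baseline and post-procedure CT, and that the mean change will be reported with its 95% CI.
- Take the SD of change from repeat-scan data if any exist, and cite the source.
- Otherwise give a range with its assumptions stated. For example, with SD 0.4 at both scans and correlation from 0 to 0.8, 20 evaluable pairs give over 99% power for a 0.61 mm3 reduction, and 90% power for reductions from about 0.43 mm3 (correlation 0) down to about 0.19 mm3 (correlation 0.8).
- State that testing is two-sided, if that is intended.

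The cost is one paragraph in a protocol amendment. Neither the number of patients nor the number of scans changes.

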11.3 The Level of Statistical Significance

A p value of <0.05 will be regarded as statistically significant.

11.4 Criteria for the Termination of the Study.

Given that this is an observational study which is recruiting patients who undergo a treatment that is already available in the NHS, we do not have specific stoppage criteria at this point in time. A Data Safety Monitoring Committee (DSMC) will convene at regular intervals, chaired by an independent specialist.

11.5 Procedure for Accounting for Missing, Unused, and Spurious Data.

The PI will be contacted at each site in case of missing or spurious data to ensure that the information collected is precise.

11.6 Procedures for Reporting any Deviation(s) from the Original Statistical Plan

Any deviation from the original plan will be discussed in the regular research team meetings and reported to the Sponsor and Funder and justified in the final report.

11.7 Inclusion in Analysis

CONFIDENTIAL Page 24 of 35 SHOCC Study IRAS: 299307

All participants will be included in the final analysis as this is a pragmatic cohort study.

CONFIDENTIAL SHOCC Study IRAS: 299307

12. DIRECT ACCESS TO SOURCE DATA/DOCUMENTS

Direct access will be granted to authorised representatives from the sponsor, host institution, and the regulatory authorities to permit study-related monitoring, audits and inspections.

13. QUALITY CONTROL AND QUALITY ASSURANCE PROCEDURES

The study will be conducted in accordance with the current approved protocol, ICH GCP, relevant regulations and standard operating procedures.

The University of Leicester operate a risk based audit programme to which this study will be subject.

The study research team (including the authors of this protocol and all local PIs) will meet online in two monthly intervals to ensure appropriate conduct of the study.

Data completion and quality will be reviewed once monthly by the CI and the study co-ordinator.

CONFIDENTIAL Page 27 of 35 SHOCC Study IRAS: 299307

14. CODES OF PRACTICE AND REGULATIONS

14.1 Ethics

This study is subject to NHS REC and HRA approvals before any patient can be recruited.

14.2 Sponsor Standard Operating Procedures

All relevant Sponsor SOPs will be followed to ensure that this study complies with all relevant legislation and guidelines

14.3 Declaration of Helsinki

The Investigator will ensure that this study is conducted in full conformity with the current revision of the Declaration of Helsinki (last amended October 2000, with additional footnotes added 2002 and 2004).

14.4 ICH Guidelines for Good Clinical Practice

The Investigator will ensure that this study is conducted in full conformity with relevant regulations and with the ICH Guidelines for Good Clinical Practice (CPMP/ICH/135/95) July 1996.

14.5 Approvals

Once Sponsor authorisation has been confirmed, the protocol, informed consent form, participant information sheet, and any study material will be submitted to an appropriate Research Ethics Committee (REC), Health Research Authority (HRA), and host institution(s) for written approval.

Once Sponsor authorisation has been confirmed, the Investigators will submit and, where necessary, obtain approval from the above parties for all substantial amendments to the original approved documents.

14.6 Participant Confidentiality

The study staff will ensure that the participants' anonymity is maintained. The participants will be identified only by initials and a participants ID number on the CRF and any electronic database. All documents will be stored securely and only accessible by study staff and authorised personnel. The study will comply with the Data Protection Act which requires data to be anonymised as soon as it is practical to do so.

14.7 Other Ethical Considerations

Some patients will be asked to participate in a sub-group analysis where post-operative computed tomographic angiograms will be performed. This involved additional radiation. At the same time, these will be limited computed tomographic angiograms which will only scan the affected area of the body, usually over a length of 30cm. This means that the radiation is minimised. Patients will be counselled with regards to this and will provide written informed consent. They will be given the chance to not participate in this part of the study should they wish, without having to offer any form of explanation.

CONFIDENTIAL Page 28 of 35 IRAS: 299307

15. DATA HANDLING AND RECORD KEEPING

All study data will be entered on a REDCap based data collection form, created specifically for the study by the National Institute for Health Research Leicester Biomedical Research Centre Bioinformatics Hub staff. As per ICH GCP (Section 5.5), all electronic data entry systems are validated and Standard Operating Procedures are maintained by the National Institute for Health Research Leicester Leicester Biomedical Research Centre.

The participants will be identified by a study specific participant number and/or code in any database. The patient's name and any other identifying detail will NOT be included in any study data electronic file. No identifiable information will be shared between study sites at any point. Consent forms (signed) will be kept in study-specific site files at the NHS institutions taking part in this research in a locked safe NHS office as per standard Good Clinical Practice guidance and NHS policies.

Cross sectional imaging including duplex scans and computed tomographic angiograms will be analysed and reported locally at each NHS site by expert radiology doctors and the reports (fully anonymised) will be uploaded on the REDCap CRFs remotely. Further, the plaque analyses will be performed locally using computed tomographic angiograms as per the agreed study protocol and the relevant results will be reported (fully anonymised) on the CRFs for each patient. Non-anonymised scans will not be shared between sites at any point.

